### **10.1 Analyzable Populations**

The All Treated Population is defined as patients who receive at least one dose of MTX or Humira in the registry. The All Treated Population will be used for analysis of safety and effectiveness.

In addition, the Intermittent Treatment Population, defined as Humira patients who have at least one treatment interruption in Humira dosing, will be used in the analysis of safety and effectiveness.

A treatment interruption (TI) for a patient will be defined as a period of > 70 consecutive days during which a patient does not receive any Humira injections. The first day of the TI will begin 71 days after the previous injection of Humira. For patients who receive another Humira injection after the TI, the last day of the TI will be defined as the day before the patient receives the next injection (i.e., the first post-TI Humira injection; see Figure 3). Note that a patient may have multiple TIs. If a patient fails to restart Humira within 1 year of the last Humira injection, then that patient will not be included in the Intermittent Treatment Population.

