### **10.3.4 Analysis of Patients with Treatment Interruption (TI)**

The following summaries will be performed for patients with a treatment interruption (TI) in Humira injections. The SAEs and AEs of Special Interest collected through the HCP process will not be included in these summaries.

For the first group of safety summaries, all patients will be categorized into 2 groups: patients who have at least one TI and patients who have no TI. Two summaries of SAEs

and Adverse Events of Special Interest will compare descriptively patients who have at least one TI and patients who have no TIs:

Crude incidence: The number and percent of patients experiencing SAEs or Adverse Events of Special Interest will be tabulated for each SOC and PT.

Events per 100 patient years of observation: The number of SAEs and Adverse Events of Special Interest per 100 patient years of observation will be tabulated for each SOC and PT.

For the second group of safety summaries the longest TI will be considered and adverse event rates (SAE and Adverse Events of Special Interest) during the last on-drug period prior to the TI (i.e., the pre-TI period) will be compared to adverse event rates during the first on drug period following the TI (i.e., the post-TI period).

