**Table 2. Definition of Pre-TI and Post-TI Periods**

	Pre-TI Period	Post-TI Period
Start	First injection of the registry	Day of first injection following the longest TI
End	70 days following the last injection before the longest TI	70 days following registry completion/stop of participation

The preceding summaries do not distinguish between the same adverse events experienced by the same patients pre-TI and post-TI from the same adverse events experienced by different patients pre-TI and post-TI. Therefore, a third summary will evaluate the proportions of patients who report onset of the same adverse event pre-TI and post-TI, patients who report onset only pre-TI, patients who report onset only post-TI, and patients who do not report the event in either period.

For each TI experienced by 1% of patients and for each SAE and Adverse Event of Special Interest, the number and percent of patients who have the event or not before the TI and after the TI will be summarized as shown in [Table 3](#). This assessment will provide information about whether same or different patients experience the adverse pre-TI and post-TI.

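### Section 10.3.4 defines the pre-TI and post-TI periods in two conflicting ways, and Table 2 lets other interruptions and restarts into both

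*Supplement*

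**What the plan says.** Protocol Section 10.1 sets the unit of analysis: "A treatment interruption (TI) for a patient will be defined as a period of > 70 consecutive days" without a Humira injection. It adds: "Note that a patient may have multiple TIs".

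Section 10.3.4 then plans several safety summaries. The second group is the before/after rate comparison, indexed on one TI per patient: "For the second group of safety summaries the longest TI will be considered and adverse event rates". The body text takes the pre-TI rate "during the last on-drug period prior to the TI (i.e., the pre-TI period") and the post-TI rate "during the first on drug period following the TI (i.e., the post-TI period").

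Table 2, in the same section, gives these limits:
- **Pre-TI start:** "First injection of the registry".
- **Pre-TI end:** "70 days following the last injection before the longest TI".
- **Post-TI start:** "Day of first injection following the longest TI".
- **Post-TI end:** 70 days after the patient completes the registry or stops participating.

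Section 10.3.4 does not say whether days and events inside another TI are removed from either period. Sections 10.3, 10.3.2 and 10.3.3 do exclude TI-period events from the treatment-emergent summaries.

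**The concern.** The text describes one on-drug stretch on each side of the index TI. Table 2 describes everything from registry start to the index TI, and everything from the restart to the end of participation. Two programmers could each follow the protocol and report different rates.

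The effect of interruptions on safety and effectiveness is part of the secondary objective (Section 5.0), and hypersensitivity to Humira injection is a listed event of special interest (Section 7.1.3). Take a patient whose longest TI is the second, and who has a reaction after the first restart. The event is scored as pre-TI under either definition, although it followed re-exposure.

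There may be a knock-on for effectiveness. Section 10.4.2 anchors on 12 weeks after the first dose of the pre-TI period. If it borrows the Section 10.3.4 definitions, that dose is the first registry injection under Table 2. Under the text it is a restart dose for a patient with an earlier TI.

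**Working it through.** **No planned figure to reproduce.** The TI summaries are descriptive; the protocol attaches no sample size, test or effect size to them. The check is a comparison of definitions, followed by an illustration of possible size.

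**Step 1: the definitions on one patient.** Let the registry history be D1 (on drug), A (short TI), D2 (on drug after restart), B (longest TI, the index), D3 (on drug after restart), C (short TI), D4 (on drug after restart).

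| Rule | Pre-TI | Post-TI |
|---|---|---|
| Text of 10.3.4 | D2 | D3 |
| Table 2 | D1 + A + D2 | D3 + C + D4 and any off-drug time to the end of participation |
| First registry TI as index, on-drug segments only | D1 | D2 |

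The text and Table 2 disagree on both sides. Table 2 includes off-drug segments (A, C) and extra restarts (D2, D4). The text removes A and C, but its pre-TI segment D2 is itself post-restart. With a single TI the two pre-TI definitions coincide.

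**Step 2: illustrative size, pre-TI side.** None of these inputs comes from the documents. The on-drug rate is 1; it is R for w years after a restart; the off-drug rate is q. Pre-TI and post-TI last 2 years each, and an earlier TI contributes 0.5 off-drug year. s is the share of TI patients whose longest TI is preceded by a shorter one.

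- Post rate = [(2 − w) + wR] / 2
- Table 2 pre rate = {(1 − s)·2 + s·[(2 − w − 0.5) + wR + 0.5q]} / 2
- Text pre rate, with a 1-year last on-drug period in affected patients = {(1 − s)·2 + s·[(1 − w) + wR]} / {(1 − s)·2 + s·1}

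Example (Table 2, R = 2, w = 0.5, q = 1, s = 0.10): post = (1.5 + 1.0)/2 = 1.25; pre = (0.9·2 + 0.1·2.5)/2 = 1.025; ratio = 1.25/1.025 = 1.22.

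| Post/pre ratio | s = 0 | 10% | 25% | 50% | 100% |
|---|---|---|---|---|---|
| Table 2, R = 2, w = 0.5, q = 1 | 1.25 | 1.22 | 1.18 | 1.11 | 1.00 |
| Table 2, R = 3, w = 0.5, q = 1 | 1.50 | 1.43 | 1.33 | 1.20 | 1.00 |
| Text, R = 2, w = 0.5 | 1.25 | 1.22 | 1.17 | 1.07 | 0.83 |
| Table 2, R = 1.5, w = 0.25, q = 0.5 | 1.06 | 1.07 | 1.08 | 1.10 | 1.13 |
| Table 2, R = 1 (no restart effect), q = 0.5 | 1.00 | 1.01 | 1.03 | 1.07 | 1.14 |

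The first three rows show attenuation, under the text's rule as well as Table 2's. The last two show the opposite: low-rate off-drug time left in the pre-TI period raises the ratio, even with no restart effect.

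**Step 3: post-TI side, same model, every patient having one later TI of 0.5 year, and a pre-TI rate of 1.**
- R = 1, q = 0.5: post = (1.5 + 0.5·0.5)/2 = 0.875, so the ratio falls from 1.00 to 0.88.
- R = 2, w = 0.5, q = 1, with a second restart in the period: post = (0.5·1 + 0.5·2 + 0.5·1 + 0.5·2)/2 = 1.50, against 1.25 with one restart.

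**Step 4: indexing on the first registry TI.** This corresponds to s = 0 on the pre-TI side, which returns the assumed effect (1.25 and 1.50 in the first two rows).

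**The case against.** A reader might infer that indexing on the longest TI dilutes any effect of restarting Humira. The documents do not support that. The pre-TI mechanism reaches only patients with at least two TIs whose longest is not the first. The protocol says multiple TIs may occur and gives no share. Step 2 also shows that the direction is not fixed.

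A reader might also attach a large figure. Suppose a rate doubling lasts for all re-exposed time, with 1 year before the first TI, 1.8 on-drug years between the first restart and the longest TI, and 1.5 pre-TI years in other patients. The reported ratio is then 2 ÷ {[(1 − s)·1.5 + s·(1 + 1.8·2)] / [(1 − s)·1.5 + s·2.8]}, which is 1.80 at s = 10% and 1.41 at s = 50%. The arithmetic is right, but the doubling is assumed to last, off-drug time is left out and the durations have no source. If TI lengths are exchangeable, the longest of two is the second half the time, so s = 50% would need nearly every TI patient to have two.

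Other points on that side have weight. The longest TI gives the largest off-drug gap, whereas a first TI may barely exceed 70 days, so the choice of main index is a trade-off. Section 10.3.4 also plans shift tables for each TI experienced by 1% of patients, same-patient before/after summaries, and a comparison of patients with and without any TI. These are partial cover: the shift tables report patient counts, not rates, and the any-TI comparison has no before/after structure.

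Finally, no SAP is shown, and segment rules are often left to it. That would answer an omission. It does not answer a protocol that states the rule twice, with different content.

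**Conclusion.** The point stands as a contradiction between the text of Section 10.3.4 and Table 2, on both the pre-TI and the post-TI period. For patients with more than one TI, Table 2 puts earlier TIs and restarts into the pre-TI period, and later TIs and off-drug time into the post-TI period. The rate comparison can be biased in either direction.

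Aligning the two is necessary but does not settle everything. When the longest TI is not the first, the pre-TI period holds re-exposed time under either definition, which usually pulls a restart effect toward 1. The loss is small if few patients are affected (1.25 to 1.22 at 10%) and larger if many are (1.11 under Table 2 or 1.07 under the text at 50%). These figures rest wholly on assumed rates, durations and shares; the documents supply none of them.

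The finding does not show that the longest TI is the wrong main index, or that every restart effect is diluted. It should be corrected before the TI summaries are produced.

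**What to change.** Make Table 2 match the text of Section 10.3.4:

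- **Pre-TI:** from the later of the first registry injection and the first injection after the preceding TI, to 70 days after the last injection before the index TI.
- **Post-TI:** from the first injection after the index TI to 70 days after the last injection before the next TI, or after the last registry dose if there is no further TI.
- **TI days:** exclude them and their events from both periods, in numerator and denominator, and say so.
- **Sensitivity analysis:** repeat the comparison indexed on each patient's first registry TI, so that the pre-TI period holds no re-exposure after a registry TI. Keep the longest TI as the main index if the sponsor prefers it.
- **Reporting:** give the number of patients with more than one TI, and the number whose longest TI is not the first.
- **Section 10.4.2:** state which definition it uses.

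The cost is protocol or SAP wording plus re-derivation from dosing and interruption dates that Section 6.6.11 already collects through Year 10. The downsides are small: shorter periods hold fewer events, so intervals widen, and the first TI may be shorter than the longest.

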#### **6.6.11 Humira and Methotrexate Treatment and Dosing Changes**

Prior to enrolling a patient into the registry, the participating Physician will provide the patient a prescription for Humira or MTX along with instructions for appropriate use. At each registry visit, the Physician will collect the start and stop dates (if applicable), any dose interruptions and reason for the dose interruption that may have occurred since the last registry visit. The dose, dates of administration, any dose interruptions or changes, and the reason for the interruption will be captured in the source documents and eCRFs. Humira and MTX registry treatments and dosing changes will be collected through registry Year 10.

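### The pre-TI versus post-TI safety rates are distorted by selection: the event that triggers an interruption is counted as pre-TI, and events that end Humira for good are lost from the pre-TI side only

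*Supplement*

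**What the plan says.** Section 10.3.4 takes the longest TI and sets SAE and AESI rates in the last on-drug period before it against those after restart: "i.e., the pre-TI period) will be compared to adverse event rates during the first on drug period following the TI". Table 2 fixes the windows. The pre-TI period starts at "First injection of the registry" and ends "70 days following the last injection before the longest TI". The post-TI period starts at the first injection after that TI and ends "70 days following registry completion/stop of participation".

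Section 10.1 defines a TI as "a period of > 70 consecutive days during which a patient does not receive any Humira injections". The TI begins on day 71, so the pre-TI window and the TI adjoin with no gap. A patient who does not restart within 1 year of the last injection is left out of the Intermittent Treatment Population.

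Section 6.6 allows interruption for any reason. Section 6.6.11 has the physician record "any dose interruptions and reason for the dose interruption that may have occurred since the last registry visit". Section 10.3.4 does not use that reason, does not flag the triggering event, and gives no sensitivity analysis.

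A further summary (Table 3) cross-classifies patients by event type: "patients who report onset of the same adverse event pre-TI and post-TI, patients who report onset only pre-TI", and so on for the remaining cells. Section 5.0 names the effect of treatment interruptions on safety and effectiveness as something to be evaluated, within its paragraph on the secondary objective.

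**The concern.** Two selections act on this comparison, in opposite directions.

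- **Triggering events.** A patient enters because an on-drug period ended in a TI. If an SAE or AESI caused the TI, it normally falls within 70 days of the last injection and so counts as pre-TI. The post-TI period ends with registry participation and need not end in an event.
- **Treatment-ending events.** A post-TI period exists only if Humira is restarted. Events that stopped Humira permanently cannot appear on the pre-TI side, but they do count after restart.

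The event definitions tighten the link. Under Section 7.1.2 a laboratory or vital-sign change can qualify as an AE because it led to a temporary or permanent stop. Under Section 7.1.3 events leading to premature discontinuation are themselves AESI.

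The risk is that a difference between the two rates is read as an effect of interrupting and restarting Humira when it arises from how the periods were chosen.

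**Working it through.** The plan states no figure for this comparison. Its one power figure (Section 10.6, about 97% for serious infections) reproduces: 1500 patient-years give 42 versus 72 expected events, and an exact two-sided 0.05 test has 97.8% power. It has no bearing here.

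**Inputs from the documents:** the Table 2 windows; a TI of more than 70 days with restart within 1 year (10.1); summaries through 10 years (10.3).

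**Assumed, because the documents do not give them:**
- λ = true event rate, the same before and after the TI: 5 to 20 per 100 PY
- p = share of on-drug events that trigger a TI followed by restart
- d = share of events that end Humira for good
- a = 0.10 per year, TIs for other reasons
- s = 0.05 per year, other permanent stops
- gap spread evenly from 70 days to 1 year, mean (0.19 + 1)/2 = 0.60 year, so L = 10 − 0.60 = 9.40 (or 4.40 at 5 years); one TI per patient

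**Formulas:**
- Share of TIs that are event-triggered: q = λp/(λp + a)
- Hazard of leaving the first on-drug period: h = λ(p + d) + a + s
- Mean pre-TI time: t = 1/h − L/(exp(hL) − 1)
- Pre-TI rate = λ(1 − p − d) + q/t. Until the period ends, only events that neither interrupt nor stop can have occurred; the trigger then adds one event for a share q of patients.
- Post-TI rate = λ, since all events count.

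**Worked case,** λ = 0.10, p = 0.10, d = 0: q = 0.01/0.11 = 0.091; h = 0.16; t = 6.25 − 9.40/(exp(1.504) − 1) = 3.56 years; pre-TI rate = 0.090 + 0.0909/3.56 = 0.1155, that is 11.6 per 100 PY against 10 after restart.

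| p | d | q (λ=10) | t (years) | Pre-TI rate (λ=10) | Pre/post, 10 y, λ 5–20 | Pre/post, 5 y, λ 5–20 |
|---|---|---|---|---|---|---|
| 0.10 | 0 | 0.091 | 3.56 | 11.6 | 1.14–1.16 | 1.33–1.39 |
| 0.30 | 0 | 0.231 | 3.43 | 13.7 | 1.28–1.44 | 1.70–2.05 |
| 0.10 | 0.10 | 0.091 | 3.50 | 10.6 | 1.05–1.07 | 1.24–1.29 |
| 0.05 | 0.10 | 0.048 | 3.53 | 9.8 | 0.98–0.99 | 1.09–1.10 |
| 0.10 | 0.30 | 0.091 | 3.37 | 8.7 | 0.87 | 1.05–1.09 |
| 0.05 | 0.30 | 0.048 | 3.40 | 7.9 | 0.79 | 0.90 |

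The true ratio is 1.0 in every row. Adding Table 2's 70-day tail by simulation pulls the values slightly toward 1 (0.80 to 1.41 over 10 years). A separate simulation with the Table 2 windows, at λ = 15 per 100 PY, p = 0.20 and d = 0, gave 18.4 versus 15.0 per 100 PY at 10 years and 23.2 versus 15.0 at 5 years. With p = 0 and d = 0 it showed no bias.

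**Dropout.** With 68% dropout by Year 5 (the figure in Section 10.6), the last four rows at 10 years move up to 1.18–1.21, 1.05–1.06, 1.00–1.01 and 0.86–0.87.

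**Does deleting the trigger solve it?** No. The pre-TI rate then falls to λ(1 − p − d). With p = 0.10 and d = 0 that is 9 against 10, a post/pre ratio of 1.11. The simulations gave 1.09 to 1.62.

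**Does the proposed contrast work?** For TIs not caused by an AE, counting only events that led to no interruption or stop gives λ(1 − p − d) in both on-drug periods. Simulated rates agreed: 6.96 versus 7.03 per 100 PY, and 6.06 versus 6.02 with permanent stops included.

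**The case against.** The strongest reply is that the direction is not fixed. A reader might infer that the plan must make restarting Humira look safer. The restart requirement argues against that: where 30% of events end treatment and 5–10% trigger a TI, the 10-year ratio falls below 1. This stands, and it is why the point is stated conditionally.

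The size can also be overstated. The 5-year ratios are larger, but these summaries run through 10 years. Only gaps above 70 days qualify, so short holds for an AE never count, and large values of p may be unrealistic. This stands too.

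Three stronger readings are tempting and are not supported.
- **That restart is compared with first treatment.** The pre-TI period begins at the first registry injection, and Section 6.1.1 admits patients with up to 24 months of earlier Humira, or longer after a sponsor study.
- **That Table 3 miscounts.** A triggering event did occur before the TI and belongs in the pre-TI row. The split of that row already shows recurrence. The table merely lacks a breakdown by reason.
- **That a rise in hypersensitivity after restart would be hidden.** Hypersensitivity to Humira injection is its own AESI in Section 7.1.3. A new case after restart falls in the No-to-Yes cell whatever other event triggered the TI.

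It is also fair that the comparison is descriptive, with no test or rate ratio specified, and that no SAP is shown, where a by-reason split might appear. Neither removes the problem: the protocol itself fixes the windows, and two rates set side by side will be compared.

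**Conclusion.** The concern holds in conditional form. As written, the pre/post rate comparison mixes any effect of interruption with two selection effects. With a constant true rate, the pre/post ratio is about 0.8 to 1.4 over 10 years for λ of 5 to 20 per 100 PY, p of 0.05 to 0.30 and d of 0 to 0.30, with other TIs at 10 and other stops at 5 per 100 PY. It is higher at 5 years.

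Under these assumptions the pre-TI rate is inflated when event-triggered TIs are as common as, or more common than, event-driven permanent stops. It is about unbiased over 10 years at p = 0.05 and d = 0.10, and reversed when permanent stops dominate. The tipping point moves with dropout and with the assumed rates of other interruptions and stops. The documents supply none of the shares, so neither the sign nor the size can be settled from them. What is certain is that the contrast does not isolate the effect of interruption, and that the reason for each TI, already collected, goes unused.

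**What to change.** In Section 10.3.4:

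1. Present the pre/post rates and Table 3 by the recorded reason for the longest TI, AE versus other (Section 6.6.11).
2. Make TIs not caused by an AE the main before/after contrast. Count in both periods only events that did not lead to interruption or permanent stop, and say so in the table title.
3. Show the all-event rates alongside, with and without the triggering event.
4. For AE-caused TIs, report the proportion whose triggering event recurs after restart, and state that the pre/post rate difference is not to be interpreted as an effect of interruption.

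Item 2 presupposes on-drug time on both sides. The text speaks of the first on-drug period after the TI, while Table 2 runs to the end of participation; these need reconciling in any case.

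Cost: protocol or SAP wording and one extra table split on data already on the eCRF. Strata are smaller and intervals wider. The main contrast leaves out events that led to interruption or stop, among them the discontinuation AESI, which is why the all-event rates are kept.

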**Table 2. Definition of Pre-TI and Post-TI Periods**

	Pre-TI Period	Post-TI Period
Start	First injection of the registry	Day of first injection following the longest TI
End	70 days following the last injection before the longest TI	70 days following registry completion/stop of participation

The preceding summaries do not distinguish between the same adverse events experienced by the same patients pre-TI and post-TI from the same adverse events experienced by different patients pre-TI and post-TI. Therefore, a third summary will evaluate the proportions of patients who report onset of the same adverse event pre-TI and post-TI, patients who report onset only pre-TI, patients who report onset only post-TI, and patients who do not report the event in either period.

For each TI experienced by 1% of patients and for each SAE and Adverse Event of Special Interest, the number and percent of patients who have the event or not before the TI and after the TI will be summarized as shown in [Table 3](#). This assessment will provide information about whether same or different patients experience the adverse pre-TI and post-TI.

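### Section 10.3.4 states an on-drug comparison before and after the longest treatment interruption, but Table 2 defines windows that can include off-drug time and other interruptions

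*Supplement*

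**What the plan says.** The second group of safety summaries in Section 10.3.4 takes each patient's longest TI and compares two rates of SAEs and AEs of special interest (AESI). One is the rate "during the last on-drug period prior to the TI (i.e., the pre-TI period"; the other is "adverse event rates during the first on drug period following the TI (i.e., the post-TI period". Both are described as on-drug periods next to the interruption.

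Table 2 then defines the same two periods by dates:

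- Pre-TI start: "First injection of the registry".
- Pre-TI end: "70 days following the last injection before the longest TI".
- Post-TI start: "Day of first injection following the longest TI".
- Post-TI end: "70 days following registry completion/stop of participation".

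Section 10.1 defines a TI as more than 70 consecutive days without a Humira injection and adds "Note that a patient may have multiple TIs". It removes from the Intermittent Treatment Population any patient who does not restart within 1 year of the last injection. Sections 6.0, 6.5 and 6.7.2 encourage patients who stop treatment to stay in the registry, with follow-up of up to 10 years.

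**The concern.** The text and the table cannot both be programmed. Three of the four boundaries in Table 2 are dosing dates. The fourth, the end of the post-TI period, is a participation date, and participation may continue long after dosing ends. The pre-TI start is a dosing date, but the wrong one whenever the patient has had an earlier, shorter TI.

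Sections 10.3.2 and 10.3.3 stop counting 70 days after the last dose and exclude events during TIs. Section 10.3.4 has no such rule.

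The effect of interruptions on safety is part of the secondary objective in Section 5.0, and this is the before-and-after rate comparison that addresses it. A post-TI rate diluted, or raised, by off-drug time could be read as a change in risk on re-treatment when none occurred.

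A second mechanism concerns patients aged 4 to 17. From Year 6, Section 6.0 and Table 1 note f limit AESI collection to a subset: heart failure, malignancies, and AEs at least possibly related to treatment or leading to its discontinuation. SAEs are still collected. The post-TI window is the later one, so it is the one more likely to run into those years.

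**Working it through.** **Step 1. The two definitions side by side.**

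| Boundary | Text of 10.3.4 | Table 2 | Consequence |
|---|---|---|---|
| Pre-TI start | Start of the last on-drug period before the longest TI | First registry injection | Earlier, shorter TIs are inside the window |
| Pre-TI end | End of that on-drug period | Last injection before the longest TI + 70 days | Tied to dosing |
| Post-TI start | Start of the first on-drug period after the longest TI | First injection after the longest TI | Agrees |
| Post-TI end | End of that on-drug period | End of participation + 70 days | Later TIs and time after a final stop are inside the window |

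**Step 2. Effect on the rate ratio.** The protocol states no figure for this comparison, so there is none to reproduce. Let f be the on-drug share of the post-TI window, counting the 70 days after the last injection as on-drug. Let g be the same share for the pre-TI window, and r the off-drug event rate divided by the on-drug rate. If the on-drug risk is the same before and after the TI and collection of events does not change, the apparent post/pre ratio is

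[f + (1 − f)r] / [g + (1 − g)r],

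which becomes f + (1 − f)r when the pre-TI window holds no earlier TI (g = 1). The true ratio is 1.00 in every case.

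**Step 3. Inputs.** The 70 days come from Table 2: 70/365.25 = 0.19 year. The timelines and r are assumptions, because the protocol gives neither.

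**Step 4. Worked example.** One year on drug after restart, then 3 years off drug in the registry:

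- on-drug time = 1 + 0.19 = 1.19 years
- Table 2 window = 1 + 3 + 0.19 = 4.19 years
- f = 1.19/4.19 = 0.284
- at r = 0.5: 0.284 + 0.716 × 0.5 = 0.64

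**Step 5. Range, with g = 1.**

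| Assumed course after restart | f | r = 0 | r = 0.5 | r = 0.75 | r = 1 |
|---|---|---|---|---|---|
| On drug to end of participation | 1.00 | 1.00 | 1.00 | 1.00 | 1.00 |
| 1 year on, 1 year off | 1.19/2.19 = 0.54 | 0.54 | 0.77 | 0.89 | 1.00 |
| 1 year on, 3 years off | 1.19/4.19 = 0.28 | 0.28 | 0.64 | 0.82 | 1.00 |
| Restart at Year 2, 1 year on, stays to Year 10 | 1.19/8.19 = 0.15 | 0.15 | 0.57 | 0.79 | 1.00 |

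If the off-drug rate were higher than the on-drug rate, the distortion would reverse. At r = 1.5, the 3-years-off case gives 0.284 + 0.716 × 1.5 = 1.36.

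**Step 6. With dosing-based windows.** If both windows cover on-drug time only, f = g = 1 and the ratio is 1.00 whatever r is.

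**The case against.** The strongest reply is the 1-year restart rule in Section 10.1. Section 10.3 assigns the intermittent-treatment AE summary to the Intermittent Treatment Population. A patient who stops for good and stays 3 more years has failed to restart within 1 year, so on a literal reading leaves that population, and off-drug time at the end is limited to about 1 year. Alternatively, the final gap of more than 70 days may itself count as the longest TI, in which case there is no post-TI injection and no post-TI period. This reply has force: the 3-year and Year-10 rows above need the rule not to apply to a final stop. It does not settle the matter. Section 10.3.4 describes its population only as patients with a TI and does not say how a final stop is handled. Later TIs remain in the window on any reading, and the 1-year-off row still gives 0.77 at r = 0.5.

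The comparison is also descriptive, with no test attached, and no separate SAP is shown. That limits the consequence but does not remove the contradiction in the protocol.

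A reader might infer more than the documents support:

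- **That re-treatment would necessarily look safer.** This needs r below 1. No off-drug rate is given, and the stopping reasons in Section 6.8.1 include AEs, lack of effectiveness and receipt of another biologic, so a lower off-drug rate is not assured. Earlier TIs in the pre-TI window would also partly offset the effect.
- **That the extra 70 days after participation are unobserved for everyone.** Section 6.6.5 and Table 1 note h provide follow-up to at least 70 days after the last dose, so for a patient on drug at exit the addition broadly matches what is collected.
- **That the Table 3 shift counts are biased in the same way.** Section 10.3.4 builds them for each TI experienced by 1% of patients, not clearly on the longest-TI windows. They count patients with an event, so a longer post-TI window would tend to raise the post-TI count.

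**Conclusion.** The contradiction between the text of Section 10.3.4 and Table 2 is real, and following Table 2 would not estimate the comparison that the text states. The post-TI window can mix on-drug and off-drug time, though it is not off-drug throughout and is wholly on-drug for patients treated to the end of participation.

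No single figure describes the distortion. Under the assumptions above, with off-drug time present and r = 0.5, the apparent ratio runs from 0.57 to 0.77 against a true 1.00. It is exactly 1.00 at r = 1 and above 1 when r exceeds 1. The lower values further assume that the 1-year restart rule does not exclude patients with a long final gap. The reduced AESI collection in Years 6–10 would lower the later rate further for patients aged 4 to 17; that effect is not in the figures.

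The point is confined to the interruption part of the secondary objective. The treatment-emergent analyses in Sections 10.3.2 and 10.3.3 have their own dosing-based limits and are not affected.

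The separate ever-TI versus never-TI grouping in the first set of summaries is a different question, and this conclusion does not rest on it.

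**What to change.** Amend Table 2 to match the text above it:

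- **Pre-TI start:** the first injection after the preceding TI, or the first registry injection if there was none.
- **Pre-TI end and post-TI start:** unchanged.
- **Post-TI end:** 70 days after the last injection before the next TI or, if there is no further TI, 70 days after the last Humira dose; in either case no later than the last contact.
- **Denominator:** state that each rate uses the person-time of its own window. Section 10.3.4 gives no denominator for this second group.
- **Final stop:** state whether a permanent stop counts as a TI when the longest is chosen, and whether the 1-year restart rule in Section 10.1 applies to it.

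An on-drug period can itself extend past Year 5, so SAEs and AESI should be reported separately in this comparison, with a note that AESI collection changes at Year 6 for patients aged 4 to 17.

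The cost is a few words in Table 2 and period derivations from dosing dates that Section 6.6.11 already collects through Year 10. The price is fewer person-years in both columns and hence wider uncertainty around each rate.
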